6.5.2. Study treatment compliance

Study stage 1: At each visit (exclusive of visit 6, 8 and 10) from visit 4 (day 5) to the end of treatment (week 12), the study site will evaluate treatment compliance.

Study stage 2: The study site will evaluate treatment compliance at each visit from visit 13 (week 18) to the end of maintenance treatment (week 48) in sub-study 1. At each visit from visit 14 (day 5 of titration) to the end of treatment (week 48) during the study stage 2, the study site will evaluate treatment compliance.

Poor compliance is defined as when actual oral dose is less than 80% of the oral dose specified in the package insert or more than 120% of the specified oral dose. The investigator will decide whether the subject with poor treatment compliance should withdraw from the study. The investigator needs to record the condition of the subject with poor treatment compliance in the original medical record and the corresponding eCRF.

Throughout the study, the study site must strictly manage the investigational product until all drugs are returned to sponsor. Any discrepancies between the drug record and the drug inventory must be reported to sponsor.

6.6. Concomitant medication and treatments

6.6.1. Medications and treatments allowed to be used

Subjects can use the following medications at therapeutic doses:

- Oral 5-ASAs compounds (e.g., mesalazine, sulfasalazine, olsalazine, balsalazide) provided that these medications have been used for at least 6 weeks and with the dose stable for at least 2 weeks prior to randomization visit.
- Oral or IV corticosteroid therapy e.g. prednisone at a stable dose ≤ 30 mg/day, budesonide dose ≤ 9 mg, methylprednisolone dose ≤ 24 mg) or equivalent dose of steroid provided the corticosteroid treatment has been used for at least 4 weeks, with a stable dose for at least 2 weeks prior to randomization visit. The dose of corticosteroid should remain stable throughout the treatment period unless the subject experiences medical conditions causing failure to tolerate the original dose of corticosteroids or continued use of the original dose of steroids will pose significant risk to the subject in the opinion of investigators. After discussing with the medical monitor, the corticosteroid could be tapered according to the subject's condition and the reason should be recorded in detail in the medical document. All subjects included in study stage 2 who meet the criteria of tapering should start corticosteroids tapering. The detailed plan for tapering is shown in below section.
- If the dose of probiotics (such as Bifidobacterium and Saccharomyces boulardii) has been stable for 2 weeks prior to the first dose of the investigational product, then, probiotics can be used.
- Antibiotics used for UC treatment (i.e., ciprofloxacin and metronidazole), provided that their dose has remained stable for 2 weeks prior to the first dose of the investigational product.

Note: The dose of all medications above should be kept stable throughout the study.

Corticosteroids tapering

Sub-study 1 of the study stage 2: After subjects are included in sub-study 1 of the study stage 2, corticosteroids tapering should be initiated. The dose of oral 5-ASA must still be kept stable. The recommended schedule for corticosteroid tapering in the study is as follows:

- If the dose of prednisone is >20 mg/day (or equivalent), it is recommended to reduce the dose at a rate of 5 mg/week until the dose reaches 20 mg/day.
- If the dose of prednisone is ≤20 mg/day (or equivalent) or reduced to 20 mg/day (or equivalent), it is recommended to reduce the dose at a rate of 2.5 mg/week until drug withdrawal.
- The dose of budesonide should be reduced at a rate of 3 mg every 3 weeks

For subjects who cannot tolerate the corticosteroid taper without recurrence of clinical symptoms, corticosteroids may be increased up to the original dose at the beginning of

induction therapy (should not exceed baseline dose). In such cases, the tapering regimen above must be reinitiated within 2 weeks.

Sub-study 2 of the study stage 2: After subjects are included in sub-study 2 of the study stage 2 and complete dose titration, the investigator can decide whether to maintain the original dose or gradually reduce the dose of corticosteroids according to the subjects' treatment course and dose of corticosteroid. If subjects have achieved clinical response at week 24, corticosteroids tapering must be initiated. The recommended plan for such reduction is the same as above.

6.6.2. Prohibited medications and treatments

Precautions to be taken into account throughout the study:

- Subjects should not receive major surgery after participating in the study.
- Subjects should not donate blood, semen or oocyte samples during the study or within 4 weeks after the last dose of the investigational product.

The following drugs are prohibited during the study:

- Any other medications used to treat UC, including those that have been approved or are being developed (5-ASA drugs or glucocorticoids are allowed to be used, but their dose should maintain stable).
- Live vaccines, except the flu vaccine (during the treatment period and within 1 month after the last dose of the investigational product).
- Chronic nonsteroidal anti-inflammatory drug (NSAID) (note: occasional use of NSAID or acetaminophen for headache, arthritis, myalgias, menstrual cramps, etc., or low-dose aspirin [81-162.5 mg] for cardiovascular prophylaxis are permitted).
- The following drugs cannot be used in the study:
 - Treatment with medications with known impact on the cardiac conduction system and QT interval prolongation, and the second degree or higher degree atrioventricular block. A list of examples of prohibited cardiac medications is provided in Table 9.
 - Marketed biologic therapies such as abatacept, infliximab, etanercept, adalimumab, anakinra, rituximab and golimumab.
 - Immunosuppressants (e.g., azathioprine, 6-mercaptopurine or cyclosporine, methotrexate, tacrolimus, sirolimus or mycophenolate mofetil).
 - Any medication administered through the rectum for UC treatment, including enemas

(e.g., 5-ASA and corticosteroids), other than required for endoscopy preparation.

- Treatment with immunoadsorption column.
- Any investigational drug other than the study treatment.
- Intravenous immunoglobulin or therapeutic plasma exchange (TPE).
- D-penicillamine, leflunomide or thalidomide.
- Treatment with lymphocyte inhibitors (natalizumab, vedolizumab, fingolimod, ozanimod or etrasimod).
- Immunosuppressants that deplete lymphocyte (such as alemtuzumab, anti-CD4, cladribine, rituximab, ocrelizumab, cyclophosphamide, mitoxantrone and daclizumab).

Table 9. Examples of Prohibited Cardiac Medications

Drug classification	Example of medication
β -blockers	Acebutolol, atenolol, betaxolol, bisoprolol, carteolol, metoprolol, nadolol, propranolol, sotalol and timolol
Calcium channel blockers	Diltiazem and verapamil
Antiarrhythmic drugs	Amiodarone, bepridil hydrochloride, disopyramide, dofetilide, dronedarone, flecainide, ibutilide, lidocaine, procainamide, propafenone, quinidine and tocainide
Drugs that prolong the QT interval	Citalopram (>20 mg/day), chlorpromazine, haloperidol, methadone and erythromycin

The investigator should record any use of concomitant medications in the original medical record and the corresponding eCRF, including the dose, specification, the route of administration, the date of administration, and the cause of administration. All information of prior medication related to UC treatment must be recorded, and the information of prior medication related to non-UC treatment within 60 days before screening must be recorded. For drugs containing a single active ingredient, their generic names should be recorded as far as possible. For drugs containing multiple ingredients, their brand names should be recorded. In addition, the daily dose should be recorded as far as possible.

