 - *Hepatitis B surface antigen (HBsAg), hepatitis B surface antibody (HBsAb) and hepatitis B core antibody (HBcAb) must be evaluated for all the patients at screening. Patients with positive hepatitis B surface antigen (HBsAg) will be excluded. HBV-DNA test should be carried out at screening if the subject is negative for Hepatitis B surface antigen, negative or positive for hepatitis B surface antibody, and positive for hepatitis B core antibody. The subject should be excluded from the study if HBV-DNA test result is positive, or he/her can be enrolled in the study in case of negative result of HBV-DNA test.
 - **An HCV viral load test should be carried out if HCV antibody (HCVAb) is positive. The subject should be excluded from the study in case of positive HCV viral load test result. If the HCV viral load test result is negative, the subject can be enrolled in the study.
- 39. The subject has any identified congenital or acquired immunodeficiency (e.g., common variable immunodeficiency, human immunodeficiency virus [HIV] infection, organ transplantation).
- 40. The subject has received any live vaccine within 30 days prior to screening, or subjects are scheduled for immunization with any live vaccine during the study or within 1 month after the last dose of the investigational product.
- 41. Positive syphilis antibody at screening.

42. Subjects with a history of more than one episode of herpes zoster, or a history of disseminated herpes zoster or disseminated herpes simplex.

Inclusion and exclusion criteria for subjects' entry into the study stage 2 from the stage 1: Inclusion criteria:

Subjects cannot enter the study stage 2 if any of the following criteria is not satisfied:

- 1. Subjects must be those with UC who participate in the study of CBP-307CN002 and have completed 12 weeks of treatment with CBP-307 or placebo in the stage 1 and have completed all the assessments (including colonoscopy) at study visit of week 12 in study stage 1.
- 2. Subjects have good compliance in stage 1, can understand all information about the study stage 2, and are able and willing to comply with the requirements specified in the study protocol.
- 3. Subjects or their legal representatives voluntarily sign informed consent forms for study stage 2.

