3.3.3. Toxicology

A series of GLP toxicological studies in preclinical species including SD rats and Cynomolgus monkeys were carried out to determine the side effects, target organs, maximum tolerated dose (MTD) and no-observed-adverse-effect level (NOAEL).

No death occurred in rats treated with a single dose of \leq 1000 mg/kg CBP-307, or 4-week repeat doses of \leq 100 mg/kg; similarly, no deaths were seen in dogs treated with a single dose of \leq 500 mg/kg, or 4-week repeat doses of 80 mg/kg. A 4-week multiple-dose study showed that the MTD for rats was >100 mg/kg, whereas the MTD for beagle dogs was \geq 80 mg/kg/day. AUC₀₋₂₄ corresponding to the MTD for rats was 154584.94 h ng/mL (in males) and 224954.18 h ng/mL (in females); while AUC₀₋₂₄ corresponding to the MTD for beagle dogs was 28547.40 h ng/mL. The NOAEL for rats was 1 mg/kg with corresponding AUC₀₋₂₄ of 1472.37 lng/mL in males and 1507.79 lng/mL in fe males. The NOAEL for beagle dogs was 1 mg/kg with corresponding AUC₀₋₂₄ of 479.90 h ng/mL.

A 13-week repeated dose toxicity study showed that in all groups of SD rats that were given oral doses of 0.1, 1, and 10 mg/kg once daily for 13 consecutive weeks, there were visible decreases in the white blood cell (WBC) count and the number of lymphocytes. These changes were considered to be related to the expected pharmacology action of CBP-307. Under the test conditions above, the NOAEL of CBP-307 was 10 mg/kg. The mean C_{max} and AUC₀₋₂₄ under this dose for 13 weeks are 3416.57 ng/mL and 30913.66 lng/m L, respectively. In Cynomolgus monkeys that were intragastrically given repeated doses of 0.1, 1, and 10 mg/kg, respectively, once daily for 13 consecutive weeks, there were visible increases in the number of neutrophils and decreases in the numbers of WBCs and lymphocytes. All these changes were related to the expected pharmacological action (immunosuppressive effect) of CBP-307. During the study, 2 animals in the 1 mg/kg dose group presented with moribund condition and were then euthanized. The cause of moribund condition was related to the aggravation of infection after

drug administration. Excluding these 2 animals, other animals had a mean C_{max} of 477.08 ng/mL and a mean AUC₀₋₂₄ of 2005.64 h·ng/mL, respectively, at NOAEL of 10 mg/kg for 13 weeks.

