An Australian study of the safety, pharmacokinetics and efficacy of repeated doses of CBP-307 administered once daily for 28 days showed that the pre-dose lymphocyte counts in the 0.15-mg and 0.25 mg groups decreased by 48.5% and 75%, respectively, after the pharmacokinetics (PK) reached steady state. The phase I clinical study of CBP-307 (administered once daily for 14 days) in Chinese healthy subjects, found that the pre-dose lymphocyte counts in the 0.1-mg and 0.2 mg groups decreased by approximately 50% and 70%, respectively, after steady state was reached. This observation is consistent to pharmacodynamic (PD) requirement for the selection of a low dose and a high dose to be administered in a phase II clinical study. From the experience in a CBP-307 phase II Crohn's disease study, 0.1 mg or 0.2mg orally administered once daily is selected. Obvious therapeutic effects could be observed only in patients treated by 0.2 mg once daily, including the clinical improvement as well as the biomarker changes in parallel. Additionally, safety data from all these different CBP-307 phase I and II studies showed that both 0.1 mg and 0.2 mg once daily administration had comparably overall safety profile.

Thus, in order to achieve the PD requirement (the reduction in lymphocyte), and meanwhile to reduce the exposure to the less effective / ineffective dose, 0.2 mg orally administered once daily is selected as an appropriate dose in this study.

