- 39. The subject has any identified congenital or acquired immunodeficiency (e.g., common variable immunodeficiency, human immunodeficiency virus [HIV] infection, organ transplantation).
- 40. The subject has received any live vaccine within 30 days prior to screening. Or subjects are scheduled for immunization with any live vaccine during the study or within 1 month after the last dose of the investigational product.
- 41. Positive syphilis antibody at screening.
- 42. Subjects with a history of more than one episode of herpes zoster, or a history of disseminated herpes zoster or disseminated herpes simplex.

5.4.2. Inclusion and exclusion criteria for subjects' entry into the study stage 2 from the stage 1:

Inclusion criteria:

Subjects cannot enter the study stage 2 if any of the following criteria is not satisfied:

- 1. Subjects must be those with UC who participate in the study of CBP-307CN002 and have completed 12 weeks of treatment with CBP-307 or placebo in the stage 1 and have completed all the assessments (including colonoscopy) at study visit of week 12 in study stage 1.
- 2. Subjects have good compliance in stage 1, can understand all information about the study stage 2, and are able and willing to comply with the requirements specified in the study protocol.
- 3. Subjects or their legal representatives voluntarily sign informed consent forms for study stage 2.
- 4. Female subjects of childbearing potential and male subjects who have not undergone vasectomy should use at least one highly effective method of contraception during the entire study and 4 weeks after the last dose of investigational products after signing the informed consent form. The highly effective methods of contraception in this study include:
 - a. Abstinence is acceptable only if it is part of the participant's regularly practiced lifestyle;
 - b. Hormone (oral, patch, ring, injection, implant) in combination with a male condom. This must be used for at least 30 days before the first dose of investigational products or an alternative acceptable method must be used;
 - c. Intrauterine device (IUD) in combination with a male condom;
 - d. Exceptions are: a) women with at least 12 consecutive months amenorrhea in the absence of medications known to induce amenorrhea and have a documented FSH level of greater than 40 mIU/mL or in the postmenopausal range; or b) surgical sterilization (e.g., hysterectomy, bilateral oophorectomy).

Exclusion criteria:

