Subjects who meet any of the following criteria will not be included in study stage 2:

- 1. The subject has any unstable or uncontrolled cardiovascular, pulmonary, hepatic, renal, GI, genitourinary, hematological, coagulation, immunological, endocrine/metabolic, or other medical disorder that, in the opinion of the investigator, would confound the study results or compromise subject safety.
- 2. Subjects who are known to be allergic to CBP-307 or its excipients, or subjects experience significant adverse events related to the study drug during the stage 1 of the CBP-307CN002 study, and the investigator deems that subjects are not appropriate to participate in the stage 2.
- 3. Subjects currently have evidence of active or untreated latent tuberculosis.

- 4. Subjects currently have active or chronic recurrent infections, and in the opinion of the investigator subjects are not appropriate to participate in stage 2 of the study.
- 5. History of uveitis or macular oedema.
- 6. Subjects had received any of the following treatments after administration of the first dose in stage 1 of the study:
 - a) Biological product;
 - b) Prednisone>30 mg/day, budesonide>9 mg/day, methylprednisolone>24 mg/day or equivalent dose of steroid treatment;
 - c) Immunosuppressant (such as azathioprine and 6-mercaptopurine or methotrexate).
- 7. Investigator deems that the 12-lead ECG results at the study visit of week 12 during study stage 1 is clinically significant abnormal, such as myocardial ischemia, any significant cardiac conduction abnormalities (such as the left bundle branch block), any abnormality that would put the subject at risk or interfere with the study results.
- 8. Pulmonary function test (including examinations of lung ventilation function and pulmonary gas exchange) of subjects at the study visit of week 12 during the study stage 1 shows 1 of the following abnormalities: forced expiratory volume in 1 second (FEV₁) or forced vital capacity (FVC) < 50% of normal predicted value.
- 9. Subjects' laboratory measurements at week 12 visit during the study stage 1 meet any of the following criteria:
 - AST or ALT> 3 ULN;
 - Absolute lymphocyte count $< 0.2 \times 10^{9} / L$;
 - Serum creatinine > 124 μ mol/L (in females) or > 141 μ mol/L (in males).
- 10. Any other reason that in the opinion of the investigator may interfere with subject compliance or evaluation of the results of the study.

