8.6. Clinical laboratory parameters and abnormal laboratory test results

Regarding major abnormal changes in laboratory parameters, which are judged by the investigator to be clinically significant, they will be recorded as AEs (except a decreased lymphocyte count, see section 8.1.1 for details).

During treatment, both the total white blood cell count and the white blood cell classification data is blinded.

If any of the following results are observed, the investigator will need to repeat the test:

- Absolute lymphocyte count $< 0.2 \times 10^9/L$
- Absolute neutrophil count $< 1.0 \times 10^{9}/L$
- Total white blood cell count $> 20 \times 10^{9}/L$

If the value of the repeated test also exceeds the above numerical limit, the investigator should be informed of the abnormal results of the subject.

If the absolute lymphocyte count or total white blood cell count is determined to be below an acceptable threshold, the medical monitor will contact the investigator responsible for treatment to ask him/her to closely monitor the event that may lead to serious infection and to follow up the subject appropriately.

If the absolute lymphocyte count is $< 0.2 \times 10^{9}$ /L, the subject should temporarily discontinue the investigational product. The absolute lymphocyte count should be retested every 3 days. If the retest result shows that the lymphocyte count rises to $> 0.5 \times 10^{9}$ /L, the investigator will be informed that the value is within the acceptable range, and the investigational product can be restarted (the statement of investigational product restart after interruption is shown in Section 6.2). If the lymphocyte count could not return to at least 0.5×10^{9} /L after 2 weeks, the investigator should discuss with sponsor and the medical director of CRO whether subjects can continue participating in the study.

Bradycardia

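### Section 6.6.2 exempts the flu vaccine from the on-study live-vaccine ban, so a live influenza vaccine not scheduled at entry is permitted although exclusion 40 has no such exception

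*Protocol*

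**What the plan says.** The protocol has two rules on live vaccines.

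- **At entry.** Exclusion 40 in section 5.4.1 reads "The subject has received any live vaccine within 30 days prior to screening. Or subjects are scheduled for immunization with any live vaccine", and continues to cover the study and 1 month after the last dose. The synopsis has the same criterion: the subject is excluded if "subjects are scheduled for immunization with any live vaccine during the study or within 1 month after the last dose". Neither place mentions influenza.
- **On study.** The list of prohibited drugs in section 6.6.2 includes "Live vaccines, except the flu vaccine (during the treatment period and within 1 month after the last dose of the investigational product". The exempted product is not described as live or inactivated.

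The SAP has no vaccine rule of its own. Sections 5.1 and 5.2 make use of a prohibited concomitant medication a major deviation in stage 1 and in stage 2 sub-study 1, so for vaccines they depend on what 6.6.2 prohibits.

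**The concern.** The two rules address the same hazard over the same forward period but differ on one product class. The entry rule treats every live vaccine as a reason to exclude. The on-study rule, as worded, lets one live vaccine through.

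The drug's pharmacology is why a live-vaccine ban is relevant. Section 5.2.2 reports that in Chinese healthy subjects dosed for 14 days "the pre-dose lymphocyte counts in the 0.1-mg and 0.2 mg groups decreased by approximately 50% and 70%, respectively, after steady state was reached". On the neutrophil, white-cell and lymphocyte changes in the 13-week monkey study, section 3.3.3 says "All these changes were related to the expected pharmacological action (immunosuppressive effect) of CBP-307". Neither statement measures the risk of a live vaccine. They explain why the sponsor wrote the ban, and why its exception should be exact.

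What is at stake is subject safety in a narrow case: a site that relies on the prohibited list could conclude that a live influenza product is acceptable for a subject on CBP-307.

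**Working it through.** No arithmetic applies, because the point depends on no sample size, effect size or error rate. The check is a comparison of the vaccine text in both documents.

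**Step 1: the two rules side by side.**

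| | Exclusion 40 | Section 6.6.2 |
|---|---|---|
| When applied | At stage 1 entry | During the study |
| What it catches | Live vaccine in the 30 days before screening, or scheduled during the study or within 1 month after the last dose | Live vaccine given during treatment or within 1 month after the last dose |
| Influenza exception | None | Yes, type not stated |

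**Step 2: what the exception can literally do.** It is carved out of the class of live vaccines. An inactivated influenza vaccine is outside that class, so the ban never reached it and the exception changes nothing for it. The only product whose status changes is a live influenza vaccine.

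**Step 3: what remains after exclusion 40.** A live influenza vaccine already scheduled at entry excludes the subject, whatever 6.6.2 says. The remaining case is a live influenza vaccine decided on after entry.

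**Step 4: does any other text prohibit that case?**

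- Exclusion 29 refers to the prohibited list in section 6.6, so it imports the exception.
- The stage 2 entry criteria contain no vaccine criterion. Stage 2 exclusion 6 opens with "Subjects had received any of the following treatments after administration of the first dose in stage 1 of the study" and then lists biologics, higher-dose steroids and immunosuppressants. Stage 2 exclusion 10 leaves room for investigator judgement but does not mention vaccines.
- The SAP deviation rules follow the protocol's prohibited list, so an exempted vaccine would not be flagged as a prohibited medication.

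None of these closes the gap. All other live vaccines are treated consistently at entry and on study.

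**The case against.** The strongest reply is that the harm depends on one reading of a loose phrase. The text says flu vaccine, not live, attenuated or nasal vaccine, and an ordinary reader would take it as permission for seasonal flu vaccination. The documents name no live influenza product and do not say that one is used at the sites. This stands as to intent and as to exposure, which is unshown. It does not remove the inconsistency, because the sentence does not express that intent.

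A reader might also infer more than the documents support:

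- **That stage 2 entry opens a separate gap because vaccines are not re-checked there.** It does not. Section 6.6.2 governs both stages equally, so the same wording decides the matter before and after week 12. For the same reason, the length of treatment, or the share of it in stage 2, does not measure the defect.
- **That the written rule is the main safeguard because sites cannot see the counts.** Section 8.6 does say "During treatment, both the total white blood cell count and the white blood cell classification data is blinded". But counts crossing the alert limits on a repeat test are disclosed (lymphocytes below 0.2, neutrophils below 1.0 or total white cells above 20 x10^9/L). When the lymphocyte or total white-cell count "is determined to be below an acceptable threshold, the medical monitor will contact the investigator responsible for treatment". Investigators also know the mechanism: sections 3.4.2 and 8.1.1 describe the expected lymphocyte fall. Concomitant medication is asked about at each visit (7.3.9), and serious and opportunistic infections are events of special interest (7.5, 8.3). These measures detect or limit harm rather than prevent a vaccination, but with them in place the primacy of the written rule is asserted, not shown.
- **That the toxicology shows a vaccine risk at the trial dose.** The monkeys received 0.1, 1 and 10 mg/kg daily. The trial dose is 0.2 mg, about 0.003 mg/kg if body weight is assumed to be 60 to 70 kg (0.2/70 = 0.0029; 0.2/60 = 0.0033). The 70% lymphocyte fall is a group figure in healthy volunteers.

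**Conclusion.** The inconsistency is real and narrow. As written, section 6.6.2 permits a live influenza vaccine that was not scheduled at entry, during treatment and for 1 month after the last dose, while exclusion 40 treats any live vaccine as a bar to entry. The conclusion rests on the literal wording and on the fact that inactivated influenza vaccine is not live. The probable intent was to allow ordinary inactivated vaccination.

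The size in subjects is unknown: the documents give no count of influenza vaccinations and no product type. A reader might infer that the sponsor deliberately allowed live influenza vaccination on an immunosuppressive drug; nothing in the documents shows that intent. Nor is there support for an effect on the primary comparison. The rule is the same in both arms and vaccination does not enter the analysis model, so no effect on the estimate, alpha or power is claimed. This is a minor subject-safety wording inconsistency, worth correcting because the correction is so cheap.

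**What to change.** Reword the bullet in section 6.6.2 so that the prohibition covers live vaccines, including live attenuated influenza vaccine, over the period it already states (treatment and 1 month after the last dose), and add that inactivated influenza vaccine is permitted. Leave exclusion 40 unchanged. The on-study rule then matches the entry rule, and the probable purpose of the exception is stated outright.

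The cost is one sentence. Visits, sample size and analysis model are untouched. The one downside is that a live influenza vaccine given on study becomes a prohibited-medication deviation, which removes that subject from the PPS under SAP sections 5.1 (stage 1) and 5.2 (stage 2 sub-study 1). FAS and mFAS membership does not depend on it.
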